#### **I.4 Analysis Population**

All analysis will be performed on an intention-to-treat (ITT), modified ITT, and per protocol population. The ITT population are patients that were randomised in the study. The modified ITT population is defined as all patients in whom a puncture resulted in the collection of a diagnostic tissue sample. Patients in which a puncture resulted in tissue collection, independent of the quality of the sample (diagnostic or not) are defined as the per protocol population.

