## SUMMARY

**Rationale:** During Endoscopic Ultrasound (EUS), tissue samples can be obtained with different techniques. Fine needle aspiration (FNA) provides a cytological specimen. With fine needle biopsy (FNB), a histological specimen is obtained, which generally results in a better diagnostic performance. However, FNB needles are stiffer and more difficult to handle, and can therefore result in less tissue acquisition.

**Objectives:** To compare the performance and diagnostic accuracy of two EUS-guided tissue acquisition devices; a 25G Echotip Ultra Fine Needle Aspiration (FNA) device and a new, more flexible 20G Echotip ProCore Fine Needle Biopsy (FNB) device.

**Study design:** International randomized multicenter trial.

**Study population:** Patients  $\geq 18$  years old, referred for EUS-guided tissue sampling of a: (I) pancreatic mass lesion, (II) lymph node, or (III) other submucosal or undefined mass (non-pancreatic),  $\geq 1$  cm in size.

**Intervention:** EUS-guided tissue acquisition by means of either the 25G Echotip Ultra FNA device, or the 20G Echotip ProCore FNB device.

**Main study parameters/endpoints:** The main endpoint is the diagnostic performance, measured against the *gold standard* diagnosis (based on the surgical resection specimen or in non-operated patients, the outcome of the diagnostic work-up (i.e. tissue sampling and imaging studies), confirmed by a compatible clinical disease course). Secondary endpoints include I. technical success, II, specimen specifics, such as; quality, presence of tissue cores, and pathological classification (cytology, cell-block, or histology), III. procedural aspects, such as; safety, the yield of a single needle pass, and the value of on-site pathological evaluation, and IV. inter-observer variation.

**Nature and extent of the burden and risks associated with participation, benefit and group relatedness:** There are no additional risks involved. Patients are referred for EUS-guided tissue acquisition, as part of the standard diagnostic work-up. Previous reports showed EUS-guided FNA and FNB sampling to be equally safe.

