## **I. STATISTICAL ANALYSIS**

### **I.1 Descriptive statistics**

Depending on distributional properties, outcome measures will be expressed as means  $\pm$  standard deviations (SD) or as medians with interquartile ranges (IQR). Missing follow-up data will be considered to be missing at random. Statistical significance will be assessed with the use of Student's t-test for normally distributed continuous data; either the chi-square test for categorical data (with Yates' correction when appropriate) or Fisher exact test for categorical data; and the median test for non-normally distributed continuous data. Data will be analysed with SPSS, Statistical Package for the Social Sciences. SPSS Inc, Chicago, Illinois.

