### **I.2 Univariate analysis**

#### **I.2.1 Primary endpoint**

Overall diagnostic accuracy will be compared between the two groups, using the Pearson's chi-squared test. Additionally, the p-value, adjusted by strata, will be calculated.

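### Both reduced analysis sets in SAP I.4 are selected on what the needle yielded, and no set is restricted to randomised patients in whom a puncture was attempted

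*SAP*

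**What the plan says.** SAP I.4 applies every analysis to three sets: "All analysis will be performed on an intention-to-treat (ITT), modified ITT, and per protocol population".

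- ITT: "The ITT population are patients that were randomised in the study".
- Modified ITT: "The modified ITT population is defined as all patients in whom a puncture resulted in the collection of a diagnostic tissue sample".
- Per protocol: "Patients in which a puncture resulted in tissue collection, independent of the quality of the sample".

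SAP I.2.1 gives the primary comparison: "Overall diagnostic accuracy will be compared between the two groups, using the Pearson's chi-squared test". I.4 does not say which of the three sets is primary for it. SAP I.2.2 compares technical success and adverse events between the arms, so these too are to be run on all three sets.

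The Protocol SUMMARY describes the patients as "referred for EUS-guided tissue sampling of a: (I) pancreatic mass lesion, (II) lymph node", or another submucosal or undefined mass, of at least 1 cm. Its rationale says that FNB needles are stiffer and harder to handle and may therefore obtain less tissue. The supplied text does not say when allocation takes place. On missing data, SAP I.1 says "Missing follow-up data will be considered to be missing at random", and I.6 says that missing data will be corrected where possible. Neither states how a patient with no needle result is scored for accuracy.

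**The concern.** A reduced set in a device trial is useful when it removes patients for reasons unrelated to the device. Here both reduced sets remove patients because of what the device did. Failing to obtain tissue is a failure of the needle. It is also one of the routes by which one needle could be less accurate in practice than the other. Per protocol removes those failures. Modified ITT removes them together with every non-diagnostic sample, and so selects on something very close to the primary outcome.

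Two of the three planned accuracy comparisons therefore answer a narrower question: how the needles compare once they have worked. If the arms differ in how often they work, those two comparisons favour the needle that fails more often. The name adds to the risk. A reader who sees modified ITT may expect a set close to ITT, but this one lies inside the per protocol set.

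The secondary endpoints are affected as well. The supplied text does not define technical success. If it means obtaining tissue, it is 100% in both arms of the per protocol set by construction.

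**Working it through.** **Step 1: order of the sets.** A diagnostic sample is a kind of tissue sample, and tissue can be collected only if a puncture was attempted. The sets therefore nest:

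modified ITT ⊂ per protocol ⊂ (puncture attempted) ⊂ ITT

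I.4 does not define the level in brackets. ITT contains all these patients, together with any who were randomised and never punctured.

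**Step 2: what selection on yield can hide.** The supplied documents give no accuracy, failure rate, sample size or power, so there is no planned figure to reproduce. All rates below are assumptions.

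Let a be the accuracy once tissue is obtained, equal in both arms, and f the share of attempts that give no tissue. An attempt without tissue counts as not accurate.

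- Accuracy among attempts = a × (1 − f)
- Accuracy per protocol = a, whatever f is

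With a = 85% and f = 2% versus 8%, take 100 attempts per arm. The arms have 98 and 92 patients with tissue. Accurate results are 98 × 0.85 = 83.3 and 92 × 0.85 = 78.2. Among attempts, accuracy is 83.3% versus 78.2%. Per protocol, it is 83.3/98 = 85% versus 78.2/92 = 85%.

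| Assumed no-tissue rate (two arms) | Accuracy among attempts | Gap among attempts | Gap per protocol |
|---|---|---|---|
| 0% vs 0% | 85.0% vs 85.0% | 0 | 0 |
| 1% vs 5% | 84.15% vs 80.75% | 3.4 points | 0 |
| 2% vs 8% | 83.3% vs 78.2% | 5.1 points | 0 |
| 0% vs 10% | 85.0% vs 76.5% | 8.5 points | 0 |

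The hidden gap is a × (difference in f). Modified ITT also drops non-diagnostic samples, so it hides any difference in diagnostic yield as well.

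**Step 3: what ITT shows, and on what condition.** ITT keeps failed attempts. If a share u of each arm is never punctured and is scored as not accurate, the ITT difference is multiplied by (1 − u). If those patients are treated as missing and left out, the difference is unchanged and only n falls, to n(1 − u).

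To size this, assume 80% versus 90% accuracy among punctured patients, 200 per arm and two-sided alpha 0.05, with

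power = Φ{[d − 1.96 √(2p̄(1 − p̄)/n)] / √[(p₁(1 − p₁) + p₂(1 − p₂))/n]}.

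For u = 5% scored as not accurate: p₁ = 0.76, p₂ = 0.855, d = 0.095, p̄ = 0.8075. The two standard errors are 0.03943 and 0.03914, and power = Φ[(0.095 − 0.0773)/0.0391] = 67.5%.

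| Never punctured | ITT difference if scored not accurate | Power if scored not accurate | Power if left out (difference stays 10 points) |
|---|---|---|---|
| 0% | 10.0 points | 80.2% | 80.2% |
| 3% | 9.7 points | 72.4% | 79.0% |
| 5% | 9.5 points | 67.5% | 78.2% |
| 10% | 9.0 points | 56.5% | 75.9% |

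The documents do not say which column applies, or whether u differs from zero.

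**The case against.** **ITT already protects the main result.** It contains every patient in whom the needle was tried, and it keeps the failures. This stands. It would be wrong to say that no set holds those patients; what is missing is a set restricted to them. The protection is partial, however, because I.4 names no primary set and asks for all analyses on all three.

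**Differential failure is not established.** The Protocol speaks of FNB needles in general, and its objectives describe the FNB device under test as a new, more flexible one. Its failure rate may equal that of the FNA device, or even be lower. This also stands: neither the size nor the direction of the hidden gap is known. But that difference is part of what the trial should reveal, and a set that removes it by definition cannot do so.

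**Never-punctured patients.** A reader might infer that they count against both needles in the ITT accuracy test and so weaken it. The documents do not support that. Nothing scores them as inaccurate, and the supplied Protocol text is a summary that is silent on the timing of allocation. If allocation follows the decision to puncture, there are hardly any such patients. If they are treated as missing, the difference does not shrink. An equal loss in both arms would favour neither needle.

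**An attempted-puncture set may itself be selected.** If the operator knows the needle before deciding to puncture, that decision can depend on the arm. This is a fair limit on the remedy and a reason to keep ITT beside it.

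**The name is a matter of taste, since I.4 defines the set.** This is partly right: the label alone changes no result. The composition of the set does.

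**Conclusion.** The point holds for the composition of the sets. As written, both reduced sets in I.4 are selected on needle yield, and attempts that gave no tissue survive only in ITT. With an assumed 85% accuracy once tissue is obtained, gaps of 3.4 to 8.5 points among attempts would be absent from the per protocol comparison, for no-tissue rates from 1% versus 5% up to 0% versus 10%. With equal no-tissue rates in the two arms and equal accuracy once tissue is obtained, nothing is hidden.

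Any dilution of the ITT difference by never-punctured patients is conditional and is not part of the finding. The fall in power from 80.2% to between 72.4% and 56.5% needs a never-punctured rate of 3% to 10%, scoring as not accurate, and the assumed accuracies and sample size. None of these is in the documents. The silence on allocation timing is not evidence that allocation is early.

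**What to change.** In SAP I.4:

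1. Define modified ITT as all randomised patients with at least one puncture attempt, analysed in the arm to which they were randomised. Attempts that gave no tissue or a non-diagnostic sample stay in the denominator and count as not accurate.
2. Report accuracy in this set beside ITT, and do not let it replace ITT.
3. Rename the present modified ITT the diagnostic-sample set and use it for description only.

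The cost is a few sentences. No extra patients or procedures are needed, only a record of whether a puncture was attempted. SAP I.6 foresees an official analysis plan before database closure, which is a natural place for the wording. There is one small downside: if the needle is known before the decision to puncture, the new set is still a selection made after randomisation, and it must be read together with ITT.

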#### **I.2.2 Secondary endpoints**

Technical success, pathological classification on which diagnosis was based, and safety (i.e. adverse events) will be compared between the two arms, using the Pearson's chi-squared test. Additionally, the p-value, adjusted by strata, will be calculated. Differences in quality and the presence of tissue cores of both arms will be tested using the non-parametric test for ordinal outcomes. Kappa values will be calculated to determine inter-observer variability among pathologists.

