### **I.3 Multivariate analysis**

To study the effect of the two methods on the different outcome measures, additional multivariate analysis will be applied, as described below.

Logistic regression will be applied to assess differences of accuracy between the two methods, adjusted for; age, indication, number of needle passes, vial number, and the presence of an on-site pathologist.

Ordinal logistic regression will be applied to assess differences of quality and presence of tissue cores between the two methods, adjusted for; age, indication, number of needle passes, vial number and the presence of an on-site pathologist.

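### The primary accuracy test is run on three unranked populations, and two of them are selected on what the randomised needle obtained

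*SAP*

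**What the plan says.** SAP section I.4 opens: "All analysis will be performed on an intention-to-treat (ITT), modified ITT, and per protocol population". It then defines the three sets.

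- ITT: "The ITT population are patients that were randomised in the study".
- Modified ITT: "The modified ITT population is defined as all patients in whom a puncture resulted in the collection of a diagnostic tissue sample".
- Per protocol: "Patients in which a puncture resulted in tissue collection, independent of the quality of the sample (diagnostic or not"). No criterion of adherence to the protocol is given.

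The primary test is in section I.2.1: "Overall diagnostic accuracy will be compared between the two groups, using the Pearson's chi-squared test". That section names no population, so the general rule of I.4 applies. Section I.2.2 lists sampling success and sample quality among the outcomes to be compared: "Technical success, pathological classification on which diagnosis was based, and safety (i.e. adverse events) will be compared between the two arms", and "Differences in quality and the presence of tissue cores of both arms will be tested using the non-parametric test for ordinal outcomes". Nothing in the supplied text ranks the three populations or says how differing results would be read. Section I.6 promises an official SAP before the database is closed; it is not among the documents supplied.

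**The concern.** The trial asks which needle more often leads to the correct diagnosis. One main way for a sampling needle to fail is to bring back nothing, or nothing diagnostic. Modified ITT removes every such patient, and per protocol removes those without tissue. Membership of both sets is settled after randomisation by something the needle can change, so the patients left in the two arms need no longer be comparable.

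The names add to the difficulty. A diagnostic sample is also a collected sample, so modified ITT is a subset of per protocol and the most selected of the three sets. Most readers would expect the reverse.

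The same rule affects secondary endpoints. If technical success means that tissue was obtained (the supplied text does not define it), it is 100% in both arms of both restricted sets. In modified ITT every patient has at least one diagnostic sample, so quality is cut off from below at patient level. Single passes or vials may still be non-diagnostic. Section I.3 describes its ordinal model in these terms: "assess differences of quality and presence of tissue cores between the two methods, adjusted for; age, indication, number of needle passes, vial number". Whether quality is analysed per patient or per vial is not stated.

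At stake is which of three accuracy results carries the conclusion if they differ.

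**Working it through.** **The plan's own figures.** There are none to reproduce. The supplied text gives no expected accuracy, yield, significance level, power or sample size. The selection problem follows from the definitions; the numbers below only show how it can act.

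**Notation and scoring (assumed).** In each arm, t = P(tissue obtained), d = P(diagnostic sample, given tissue) and c = P(correct diagnosis, given a diagnostic sample). Patients with no tissue or a non-diagnostic sample count as not accurate. Then:

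- ITT accuracy = t × d × c
- Per-protocol accuracy = d × c = ITT accuracy / t
- Modified ITT accuracy = c = ITT accuracy / (t × d)

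Each restricted set divides an arm's ITT accuracy by that arm's own yield. If yields differ, the two arms are divided by different numbers.

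**Illustration (assumed rates).** 200 per arm, two-sided 5%. Needle A has t/d/c = .95/.85/.96 and needle B has .97/.92/.96.

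| Set | Needle A | Needle B | Difference (B − A) | Rejects in about |
|---|---|---|---|---|
| ITT | .95 × .85 × .96 = .775 | .97 × .92 × .96 = .857 | 8.2 points | 56% |
| Per protocol | .85 × .96 = .816 | .92 × .96 = .883 | 6.7 points | 46% |
| Modified ITT | .960 | .960 | 0 | 5% |

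The rejection rates come from simulated trials using the uncorrected Pearson chi-squared test. A normal approximation confirms the ITT figure:

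- Pooled proportion .816, so the null standard error is √(2 × .816 × .184 / 200) = .0388.
- Standard error under the assumed rates: √((.775 × .225 + .857 × .143) / 200) = .0385.
- Power = Φ((.0815 − 1.96 × .0388) / .0385) = Φ(0.14) = 56%.

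In this example needle B is better only because it more often obtains a diagnostic sample. Modified ITT discards exactly that advantage. The zero follows from setting c equal in both arms; it is not a prediction.

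**Direction.** Other assumed rates move the result the other way. With .99/.85/.94 against .93/.85/.97:

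- ITT: .767 − .791 = −2.4 points
- Per protocol: .8245 − .799 = +2.55 points
- Modified ITT: .97 − .94 = +3 points

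This reversal needs a 6-point gap in tissue yield together with a higher c in the low-yield arm.

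**Dependence on scoring.** If non-diagnostic and failed punctures were left out of the ITT denominator, accuracy among the remaining patients would equal the modified ITT figure. Naming ITT as primary therefore settles the matter only if the scoring is stated too.

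**The case against.** The strongest reply is that the valid analysis is already in the plan. ITT contains everyone randomised. Technical success is compared between arms and, under I.4, also on ITT, so a yield gap would show there if that endpoint means tissue obtained. Showing results in restricted sets is common practice, and a ranking normally goes into a full SAP, which section I.6 promises. Only the summary of the Protocol was supplied, so missing definitions of technical success and of scoring may reflect the extract.

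Most of this stands, and it limits the point. No data are lost and no valid analysis is absent. What remains is that a visible yield gap neither corrects conditional accuracy nor says which accuracy result decides, and that I.4 does not mark the restricted sets as supportive. The silence on scoring is best put to the sponsor as a request for clarification.

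Three stronger readings are tempting, and the documents do not support them.

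- A reader might infer that three tests inflate the false-positive rate. That requires significance in any one set to count as success, and no such rule is stated.
- A reader might infer a bias in favour of one needle. The Protocol summary says FNB needles in general can acquire less tissue, but describes the trial's FNB needle as more flexible, so the direction of any yield gap is unknown.
- A reader might take disagreement between the three significance verdicts as harm in itself. Nested sets of different size that answer different questions need not agree, and the zero in modified ITT above is built in by the assumption on c.

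**Conclusion.** The point holds in a limited form. As written, section I.4 gives two accuracy comparisons selected on the result of the randomised needle the same standing as the ITT comparison for the primary endpoint. That conclusion rests on the definitions alone and is secure for the text supplied.

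The size and direction of any distortion cannot be obtained from the documents. The shift from 8.2 points to 6.7 and to 0 rests entirely on assumed rates, 200 per arm, a 5% level and failures counted as inaccurate. A reversal of sign between ITT and per protocol needs a much larger yield gap than the 2 points in that illustration.

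Because ITT is planned and a later SAP may already rank the sets, this should be corrected, but it is not a defect that by itself undermines the trial.

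**What to change.** In section I.4:

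1. Name ITT, by allocated needle, as the single primary population for diagnostic accuracy.
2. State that an attempted puncture yielding no tissue or a non-diagnostic sample counts as not accurately diagnosed.
3. Keep the existing modified ITT and per-protocol results, labelled supportive, conditional on yield and non-decisive, and report them beside the ITT comparison of yield.
4. Compare technical success and sample quality between arms on ITT, not inside sets defined by those same results.
5. Have the sponsor specify how never-punctured patients and patients without a reference diagnosis are handled, with a sensitivity analysis for each. Several choices are defensible.

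If the official SAP already contains these statements, citing it is enough.

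The cost is SAP wording, with no new data. Headline accuracy in both arms will be lower than with failures removed: in the illustration, 77.5% and 85.7% on ITT against 96% in modified ITT. Any sample-size assumption (none is in the supplied text) should be checked against this scoring.

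### The per protocol set does not require that the allocated needle was used, and the modified ITT set has the same gap

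*SAP*

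**What the plan says.** The Protocol summary defines the intervention as "EUS-guided tissue acquisition by means of either the 25G Echotip Ultra FNA device, or the 20G Echotip ProCore FNB device", in an "International randomized multicenter trial". The objective is to compare these two devices.

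SAP section I.4 names three analysis populations. ITT is all randomised patients. Modified ITT is patients in whom some puncture yielded a diagnostic sample. The third, per protocol, is worded: "Patients in which a puncture resulted in tissue collection, independent of the quality of the sample (diagnostic or not) are defined as the per protocol".

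For the primary endpoint, section I.2.1 states: "Overall diagnostic accuracy will be compared between the two groups, using the Pearson's chi-squared test". Section I.2.2 states: "Technical success, pathological classification on which diagnosis was based, and safety (i.e. adverse events) will be compared between the two arms". The regression of accuracy in section I.3 compares the two methods, "adjusted for; age, indication, number of needle passes, vial number, and the presence of an on-site pathologist".

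**The concern.** A per protocol set normally holds patients who received what they were allocated. Here the only entry condition is that tissue was obtained. Whether it was obtained with the allocated device plays no part, so the set has no adherence criterion.

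If some patients were punctured with the other needle, for example after a failed attempt, the set would mix tissue from both devices within an arm. The reader would have no planned population in which each arm reflects its own needle alone. Ease of handling and tissue acquisition are part of what is being compared: the Protocol's rationale says of the class that "FNB needles are stiffer and more difficult to handle, and can therefore result in less tissue acquisition". A second needle used after a failure could mask that property.

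**Working it through.** **Step 1. Apply the definitions to a test case.** Take a patient randomised to the 20G FNB device whose only tissue, of diagnostic quality, came from the 25G FNA device.

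| Set (SAP I.4) | Condition for entry | Condition on needle | Patient included? |
|---|---|---|---|
| ITT | randomised | none, and none needed | yes, correctly |
| Modified ITT | some puncture gave a diagnostic sample | none | yes |
| Per protocol | some puncture gave tissue of any quality | none | yes |

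**Step 2. Look for the condition elsewhere.** The Protocol summary says "The main endpoint is the diagnostic performance, measured against the *gold standard* diagnosis" but not which needle's sample counts. I.2.1 and I.2.2 compare groups or arms without a rule for a second needle. The I.3 covariates include the number of passes but not the needle used or a change of needle. Nothing visible supplies the missing condition.

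**Step 3. Possible effect in the per protocol set.** The documents give no sample size, power, accuracy, failure or switch rates, so there is no plan figure to reproduce. Every input below is an assumption. It is also assumed that patients stay in their randomised arm, that every switched patient yields tissue, and that unswitched failures yield none.

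Let f be the share of an arm in which the allocated needle obtains no tissue, and s the share of those switched. The fraction of the set as written whose tissue came from the other needle is w = f·s / (1 − f + f·s). The arm's accuracy shifts by w × (rescue accuracy − own accuracy).

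- FNB, f = 10%, s = 75%: w = 0.075/0.975 = 7.7%.
- FNA, f = 3%, s = 75%: w = 0.0225/0.9925 = 2.3%.
- Needle accuracies of 75% and 85%, each needle keeping its own accuracy in rescue: shifts of 0.77 and 0.23 points towards each other. A 10.0-point difference reads as 10.0 − 0.77 − 0.23 = 9.0, whichever needle is better.
- Both needles 80% accurate but only 50% in rescue: shifts of 0.077 × (−30) = −2.3 and 0.023 × (−30) = −0.7 points, a spurious 1.6 points against FNB.
- s = 0: w = 0, no effect.

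**Step 4. Possible effect on accuracy in all randomised patients, if a rescued sample were scored for the allocated arm.** The net shift for FNB relative to FNA is (f_FNB − f_FNA) × s × a, where a is rescue accuracy.

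- (0.10 − 0.03) × 0.75 × 0.80 = +4.2 points.
- Equal failure rates: 0. Failure rates exchanged between the arms: −4.2 points.
- Smallest and largest of a wider set of inputs: (0.05 − 0.02) × 0.5 × 0.7 = 1.05 and (0.15 − 0.03) × 1.0 × 0.9 = 10.8 points. The sign follows whichever needle is assumed to fail more.

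A second illustration treats any inaccurate result as a failure. Observed accuracy is p + (1 − p)·s·r, with r the other needle's accuracy, true values of 75% and 85%, 250 per arm and two-sided alpha 0.05.

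| s | Lower arm | Higher arm | Difference | Power |
|---|---|---|---|---|
| 0 | 75.0% | 85.0% | 10.0 | 80% |
| 10% | 77.1% | 86.1% | 9.0 | 74% |
| 25% | 80.3% | 87.8% | 7.5 | 63% |
| 50% | 85.6% | 90.6% | 5.0 | 41% |

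Steps 3 and 4 show how the result depends on the unknowns. They are not estimates for this trial.

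**The case against.** The strongest reply is that no visible text mentions a change of needle, crossover or rescue sampling. Given the either/or wording of the intervention, a puncture in I.4 may have been meant as one with the allocated device. Only a summary of the protocol is visible, so a rule may exist elsewhere, and section I.6 promises an official SAP before the database is closed. This stands as a limit on what can be claimed. It does not supply the condition: I.4 states an explicit entry rule, and that rule says nothing about the needle.

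A reader might infer that rescued samples are credited to the allocated arm. No attribution rule is written, so this is possible but not documented.

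A reader might also infer that the ITT set is at fault. It is not. Keeping switched patients in their randomised arm is what ITT requires, and any gap there concerns which sample is scored.

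A reader might further infer a bias in favour of FNB, because FNB needles are described as stiffer. That sentence is about FNB needles in general, and the Protocol's objective calls the tested 20G device new and more flexible. The direction is not supported.

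Nor is it certain that switching would go unseen. Single-pass yield is a listed secondary endpoint and technical success is compared between arms, so either might show early failures. Neither removes switched patients from the per protocol set.

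**Conclusion.** The point holds as a defect of definition. As written, the per protocol set would retain any patient whose tissue came from the non-allocated needle, and the modified ITT set likewise. The conclusion rests on the text of I.4 and on the absence of a needle condition in the visible sections.

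The size and direction of any bias are unknown. With no switching, the effect is nil. The illustrative figures rest wholly on assumed rates, and their sign changes with those rates.

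The documents do not support going further and requiring the primary analysis to score every switch as a misdiagnosis. Overall accuracy by randomised arm is a legitimate target. Counting each switch as a failure would also make the primary result depend on the operator's decision to switch. That analysis belongs in a supporting role, specified in advance.

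**What to change.** - In I.4, define per protocol as patients sampled with the allocated needle only. State in the modified ITT definition whether a puncture with the other needle qualifies.
- Keep ITT by randomised arm, and say so.
- Record the needle used for each pass, if the case report form does not already do so, and report the number of switches per arm.
- Pre-specify a supporting analysis of accuracy and technical success in all randomised patients that counts only tissue obtained with the allocated needle.
- Tabulate adverse events by arm, as planned, and also by needle or needles actually used.

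This changes how samples are counted, not what is done to patients. It can go into the official SAP that I.6 promises. The cost is some SAP wording, one case report form field, a slightly smaller per protocol set, and accuracy in the supporting analysis that may be lower than overall accuracy. If no needle was changed, the results are the same as under the present definitions.
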